8. ANALYSIS SECONDARY

- Compare malaria antibody levels to other antigens between severe and non-severe COVID-19 cases:
 - A similar model to the one for the primary objective is fitted with the respective malaria antibody levels as the independent variable.
- Compare the cellular response against malaria between severe and non-severe COVID-19 cases:
 - A conditional logistic regression model will be fitted with the cellular response to malaria as the independent variable.
- Compare the proportions of acute malaria infection between severe and non-severe cases of COVID-19 using the Thick Gauge (TG) and Rapid Diagnostic Test (RDT):
 - A conditional logistic regression model will be fitted with acute malaria infection as the independent variable.

Note: Acute infection will be assessed in 3 ways: first with the EWG alone, then the RDT alone and finally the EWG or RDT taken together.

- Describe the clinical characteristics and clinical status of severe and non-severe cases of COVID-19 with and without malaria (former exposure or active infection):
 - Medians with quartiles or frequencies and proportions will be presented in 3 types of tables:
 - ▶ Cases versus controls
 - ▶ Malaria present versus malaria absent
 - ▶ Malaria cases present/absent versus Controls-Malaria present/absent

Statistical comparisons between groups (cases versus controls and malaria present versus absent) will be performed. The Fisher's exact statistical test or Chi-square test will be used to compare categorical clinical characteristics and the non-parametric Man-Whitney test for numerical characteristics.

- To assess the modulating impact of existing antimalarial immunity on the strength of humoral and cellular immune responses to SARS-COV-2 in severe and non-severe cases of COVID-19
 - The Spearman correlation between malaria immunity and immune responses to SARS-COV-2 will be calculated with a 95% confidence interval. separately for cases and controls
- Compare the SARS-COV-2 specific cellular immune response between severe and non-severe cases
 - A conditional logistic regression model will be fitted with the SARS-COV-2 specific cellular immune response as the independent variable
- Assessing the modulatory impact of antimalarial immunity on induced immunity using specific antiviral receptor stimulations of the innate immune system
 - The Spearman correlation between malaria immunity and induced immunity will be calculated with a 95% confidence interval separately for cases and controls

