2.2. OBJECTIVES

THE MAIN OBJECTIVE:

is to investigate whether the immunity conferred by Plasmodium protects against severe forms of COVID-19. This will be done by comparing Plasmodium antibody levels in severe and non-severe COVID-19 cases.

SECONDARY OBJECTIVES

They are :

- Comparing the cellular response against malaria between severe and non-severe COVID-19 cases
- To compare the proportions of acute malaria infection between severe and non-severe cases of COVID-19 using the Thick Gauge (TG) and Rapid Diagnostic Test (RDT)
- Describe the clinical characteristics and status of severe and non-severe cases of COVID-19 with and without malaria exposure
- To assess the modulating impact of existing antimalarial immunity on the strength of humoral and cellular immune responses to SARS-COV-2 in severe and non-severe cases of COVID-19
- Compare the SARS-COV-2 specific cellular immune response between severe and non-severe cases
- Assessing the modulatory impact of antimalarial immunity on induced immunity using specific antiviral receptor stimulations of the innate immune system

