4. VARIABLES OF INTEREST**4.1. PRIMARY VARIABLES OF INTEREST :**

The primary variable of interest in the study is the level of anti-malarial antibodies in severe and non-severe COVID-19 cases. This level will be assessed by measuring the concentration of IgG against Circum Sporozoite Protein (CSP) using the Luminex-MAGPIX.

4.2. SECONDARY VARIABLES OF INTEREST :

- Anti-malarial IgG antibody levels against other antigens: AMAI, CSPM, GLURP, *Pf/RESA55*, as well as IgM antibodies

- Cellular response against malaria between severe and non-severe COVID-19 cases, measured by IFN-γ ELISPOT
- The proportions of acute malaria infection between severe and non-severe cases of COVID-19 using the Thick Gauge (TG) and Rapid Diagnostic Test (RDT). Indicator variables will be used for a positive RDT result, for a positive EW result and for a positive result with both tests
- Clinical features :
 - Duration of symptoms
 - Type of symptoms
 - Size
 - Weight
 - Blood pressure
 - Heart Rate
 - Respiratory Rate (RR)
 - Temperature (T°)
 - Free Oxygen Saturation (SaO2)
 - Splenomegaly

and clinical status of severe and non-severe cases of COVID-19 with and without malaria.

The clinical status of COVID-19 only controls is assessed by the WHO 10-point clinical progression score at 7^{ème} days of follow-up¹ :

Patient's condition	Description	Score
Not infected	Not infected; no viral RNA detected	0
Ambulatory: illness benign	Asymptomatic; viral RNA detected	1
	Symptomatic; independent patient	2
	Symptomatic; need for assistance	3
Hospitalized: moderate illness	Hospitalized; no oxygen therapy	4
	Inpatient; oxygen therapy by mask or nasal route	5
Hospitalized: illness severe	Inpatient; high flow oxygen therapy	6
	Intubation and mechanical ventilation, $pO2/FiO2 \geq 150$ or $SpO2/FiO2 \geq 200$	7
	Mechanical ventilation $pO2/FIO2 < 150$ ($SpO2/FiO2 < 200$) or vasopressors	8

	Mechanical ventilation pO ₂ /FiO ₂ <150 and vasopressors, dialysis, or ECMO	9
Deaths	Deaths	10

- SARS-COV-2 specific cellular and humoral immune response of severe and non-severe cases, measured by Luminex and ELISPOT.
- Induced immunity: Levels of antiviral cytokine release, measured by ELISA and flow cytometry, of peripheral blood monocytes (PBMC) from controls and patients with acute malaria infection (according to GE and RDT).

4.3. EXPLORATORY VARIABLES OF INTEREST :

- The proportion of patients infected with urinary and intestinal parasites.

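### SAP 8 tests clinical characteristics by malaria status without separating severe cases from non-severe controls, so the test partly restates any malaria–severity association at a weight set by recruitment

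*SAP*

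**What the plan says.** The objective in SAP 2.2 is "Describe the clinical characteristics and status of severe and non-severe cases of COVID-19 with and without malaria exposure". SAP 8 serves it with three tables: cases against controls, malaria present against absent, and a split by both, labelled "Malaria cases present/absent versus Controls-Malaria present/absent".

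SAP 8 then adds tests: "Statistical comparisons between groups (cases versus controls and malaria present versus absent) will be performed". The methods are unstratified: "The Fisher's exact statistical test or Chi-square test will be used to compare categorical clinical characteristics", and "the non-parametric Man-Whitney test for numerical characteristics". No test is named for the third table. Protocol 7.2 planned only medians with quartiles or numbers and proportions for this objective, so the tests are an SAP addition.

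The variables in SAP 4.2 include "Free Oxygen Saturation (SaO2"), respiratory rate, temperature and type of symptoms. In SAP Table 1, a case needs signs of pneumonia plus a respiratory rate above 30, severe respiratory distress or saturation below 90%. A control must have no signs of severe pneumonia.

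Elsewhere in SAP 8, the Spearman correlation between malaria immunity and the SARS-CoV-2 response "will be calculated with a 95% confidence interval. separately for cases and controls". The clinical comparison carries no such instruction.

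**The concern.** The malaria-present and malaria-absent groups each mix severe and non-severe patients. Where malaria status is associated with severity, the two mixes differ. Saturation, respiratory rate and symptoms then differ too, even if malaria makes no difference among cases or among controls.

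The malaria–severity association is already addressed by conditional logistic regression in SAP 7 and 8. The pooled clinical test partly repeats it, without the matching and with the proportion of severe patients set by the recruitment ratio. The risk is that a small p-value for saturation by malaria status is read as separate evidence about clinical presentation, when it may carry no information beyond the case-control comparison.

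**Working it through.** **1. The plan's own figure.** The documents give no power or effect size for the clinical comparisons. The only planned effect is in Protocol 5.1.5: log anti-CSP means of 6.8 in controls and 6.61 in cases, SD 1, correlation 0.7, 100 cases and 200 controls, power 0.81. It reproduces. The variance of a case minus the mean of its two controls is 1 + (1 + 0.7)/2 − 2 × 0.7 = 0.45, and Φ(0.19/√(0.45/100) − 1.96) = Φ(0.87) = 0.81. This figure concerns the primary analysis. It is used here only as the source of a document-based effect, the 0.19 log difference.

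**2. Odds ratio implied by that effect.** SAP 8 gives no cut-off for former exposure, so assume one that leaves 20% or 50% of controls 'present'.
- 20% of controls: the cut-off is 0.842 SD above the control mean. In cases, 1 − Φ(0.842 + 0.19) = 15.1%. OR = (0.151/0.849)/(0.20/0.80) = 0.71.
- 50% of controls: in cases, 1 − Φ(0.19) = 42.5%. OR = (0.425/0.575)/(0.50/0.50) = 0.74.

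**3. Expected pooled difference with no malaria effect within either group.** Assumed, not in the documents: mean saturation 85 (SD 5) in cases and 97 (SD 1.5) in controls. The gap is 12 points, so the pooled difference = 12 × (share severe without malaria − share severe with malaria).

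| Present in controls / cases | OR | Ratio | Severe, malaria present | Severe, malaria absent | Difference (points) |
|---|---|---|---|---|---|
| 20% / 15.1% | 0.71 | 1:1 | 43.04% | 51.48% | 1.01 |
| 20% / 15.1% | 0.71 | 1:2 | 27.42% | 34.66% | 0.87 |
| 50% / 42.5% | 0.74 | 1:1 | 45.93% | 53.50% | 0.91 |
| 50% / 42.5% | 0.74 | 1:2 | 29.81% | 36.52% | 0.81 |
| 50% / 33.3% | 0.5 (assumed) | 1:1 | 40.0% | 57.1% | 2.06 |
| 50% / 33.3% | 0.5 (assumed) | 1:2 | 25.0% | 40.0% | 1.80 |

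**4. Rejection rates.** Simulated with the same inputs, 100 cases, 100 or 200 controls, two-sided 5%, good to about two percentage points:
- OR 1: pooled Mann-Whitney about 5%.
- OR 0.71–0.74: pooled about 12–17%, with a mean difference of about 0.8–1.05 points.
- OR 0.5, 20–50% malaria in controls: pooled about 30–58%.
- Tests within cases and within controls: near 5% throughout.

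**5. Dependence on the recruitment ratio.** SAP 8 tabulates medians. With OR 0.5, 50% malaria and a case SD of 4, the pooled median difference is 0.8 points at 1:2 and 5.9 points at 1:1. The ratio alone produces that change.

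For comparison, take OR 0.5 and 40% malaria in controls (25% in cases), and suppose 5% of infections were severe. The severe shares are 0.05 × 0.25/(0.05 × 0.25 + 0.95 × 0.40) = 3.2% with malaria and 0.05 × 0.75/(0.05 × 0.75 + 0.95 × 0.60) = 6.2% without. The difference is 12 × 0.030 = 0.36 points, against 2.05 at 1:1 and 1.76 at 1:2.

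**The case against.** **The text.** SAP 8 never says that the groups are pooled, and the label of the third table is hard to read. The authors may have meant tests within severity. But the SAP lists the split table separately, names no test for it, and asks for separation by case status only for the correlations. As written, the malaria test is unseparated.

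**The purpose.** The objective is descriptive, the SAP does not call the difference a malaria effect, and the third table lets a reader see the within-group pattern. All of this stands and limits the harm to misreading of p-values.

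**The size.** A reader might infer that about half of such studies would give a significant pooled result. That needs an odds ratio near 0.5, which the documents do not contain. Their planned effect implies the lower figures.

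**The direction.** A reader might infer that the study hypothesis makes malaria rarer in cases. SAP 3 speaks of antimalarial immunity. Malaria in SAP 8 covers former exposure or active infection, and no direction is given for active infection.

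**Spurious or not.** A reader might also infer that any pooled difference is false. If malaria does lower the risk of severe disease, malaria-positive patients do have better saturation overall. What is artificial is the weight, and so the size. Within-group tests are not neutral either, because they condition on a status partly defined by saturation and respiratory rate.

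**Scope.** Size, weight, blood pressure and splenomegaly do not define case status, so the documents give no reason to drop the pooled table.

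**Conclusion.** The point holds as a conditional one. The malaria test in SAP 8 runs across severe cases and non-severe controls in a mix set by recruitment, which the two documents state differently. If malaria status and severity are associated, the test partly restates that association at an artificial weight. If they are not, it keeps its 5% level.

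At the effect implied by the protocol, the illustration gives rejection in about 12–17% of studies and a difference of about 0.8–1.05 saturation points. It rises to about 30–58% at an assumed odds ratio of 0.5. The saturation distributions, malaria prevalence and cut-offs are assumptions, so these percentages are illustrative. The mechanism does not depend on them. The primary analysis is unaffected. This is an inexpensive improvement to a descriptive secondary objective.

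**What to change.** In SAP 8, state that the malaria present/absent tests are run separately within cases and within controls, using the third table already planned, or with a test stratified by case status. Keep the pooled malaria table as description without p-values, at least for saturation, respiratory rate, temperature and symptoms. State that within-group results are conditional on case status and are descriptive, not estimates of the total effect of malaria.

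The change needs SAP wording only and no new data. The cost is fewer participants in each within-group test than in the pooled one.

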5.2. DESCRIPTION OF

Controls will consist of asymptomatic or symptomatic cases without signs of severity. For each case, a control will be recruited after being matched in terms of age (plus or minus 10 years), gender and

Health Zone of origin. The time to recruit a control is up to 10 weeks after case recruitment.

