6.2. ANALYSIS POPULATION SECONDARY

Only participants who did not violate any major criteria will be included in the secondary analysis (see Table 1).

Table 1:Protocol violationsclassified as minor or major

Violation of the	Minor/major violation	Comments
Protocol Inclusion		
For CAS Criteria		
1. At least 18 years of age	Major	
2. Having an SARS-CoV infection confirmed by RT-PCR or rapid antigen test within 72 hours of inclusion.	Major	
3. Have given their informed consent or that of their guardian/ representative to participate in the study.	Major	
4. Clinical signs of pneumonia: fever, cough, dyspnea or crepitations and (Respiratory rate > 30 cycles/min or severe respiratory distress or SpO2 < 90% on room air)	Major	
5. Being admitted to a care unit for COVID-19	Major	
6. Reside in the health zone for at least 6 months	Minor	

For WITNESSES

1. Be at least 18 years old	Major
2. Have a PCR or antigenic test confirmed SARS-CoV- 2 infection within 72 hours prior to inclusion.	Major
3. Have given informed consent to participate in the study	Major
4. Be asymptomatic or symptomatic, but without any signs of severe pneumonia	Major
5. Not to be admitted to a care unit for COVID-19.	Major
6. Reside in the study health area for at least 6 months	Minor

Exclusion Criteria (CASES AND WITNESSES)

1. The subject has a contraindication at venipuncture, determined by clinical judgment	Major
2. The subject is vaccinated against SARS- CoV-2	Major
3. The subject has been infected with SARS- CoV-2 in the past and now presents with a reinfection	Major

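### SAP section 8 tests clinical characteristics of matched cases and controls as if the groups were independent, and exempts neither respiratory rate nor SpO2, which help define a case

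*SAP*

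**What the plan says.** SAP section 8 plans tables of clinical characteristics and then adds testing: "Statistical comparisons between groups (cases versus controls and malaria present versus absent) will be performed". The methods are Fisher's "exact statistical test or Chi-square test will be used to compare categorical clinical characteristics and the non-parametric Man-Whitney test for numerical characteristics". No paired or conditional version is mentioned.

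The design is individually matched. SAP 5.2 states: "For each case, a control will be recruited after being matched in terms of age", together with sex and health zone. The SAP's other tested case-control comparisons all use conditional logistic regression: the primary analysis (section 7), the other antigens, malaria cellular response, acute malaria and SARS-CoV-2 cellular response (section 8), and parasites (section 9). For the clinical-characteristics objective, protocol 7.2 plans only medians, quartiles, counts and proportions.

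SAP 4.2 lists respiratory rate and oxygen saturation (written SaO2, read here as the SpO2 of the eligibility criteria) among the clinical features, and section 8 exempts neither from testing. In SAP Table 1 a case needs signs of pneumonia plus one of these: "Respiratory rate > 30 cycles/min or severe respiratory distress or SpO2 < 90% on room air". A control must "Be asymptomatic or symptomatic, but without any signs of severe pneumonia"; protocol 5.1.1 lists the same three signs there. Breach of either criterion is major, and SAP 6.2 says: "Only participants who did not violate any major criteria will be included in the secondary analysis".

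**The concern.** There are two separate problems in one table.

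First, matching makes a case and its control resemble each other to some degree. A test that treats them as unrelated overstates the variance of the difference, so its p-values are too large and real differences can be missed. The SAP handles this correctly elsewhere and gives no reason for departing here.

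Second, a p-value comparing cases and controls on respiratory rate or SpO2 is computed on groups formed partly by those measurements. A small p-value in those rows can arise from the eligibility rules alone and could be read in a publication as a clinical finding.

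**Working it through.** **Inputs from the documents.** Individual matching (SAP 2.1, 5.2); one control per case in SAP 5.2, two in protocol 5.1.4, so both ratios are considered; 100 cases and a two-sided 5% level (protocol 5.1.5, stated there for the primary test).

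**Assumed, because the documents do not give them.** Within-set correlation ρ of clinical variables, 0 to 0.3; normal data; a difference of 0.3 SD; random loss of 0 to 30% of participants per arm; the share q of cases whose SpO2 lies below that of every control, 10 to 50%.

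**Step 1: the plan's own figure.** The only power calculation is for the primary antibody analysis: 0.81 with 1:2 matching, SD 1, correlation 0.7 and log means 6.8 and 6.61. The variance of a case minus the mean of its two controls is 1 + (1 + 0.7)/2 − 2 × 0.7 = 0.45. SE = √(0.45/100) = 0.0671. Power = Φ(0.19/0.0671 − 1.96) = 0.81, and simulated conditional logistic regression gives 0.797. The figure reproduces. Its correlation of 0.7 is for log antibody level and is not used below.

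**Step 2: size of the planned test.** Matching multiplies the variance of the mean difference by (1 − ρ) in either ratio: 2 − 2ρ against 2 for 1:1, and 1.5 − 1.5ρ against 1.5 for 1:2. For ranks, ρ is replaced by r = (6/π) asin(ρ/2). The true size of a nominal 5% Mann-Whitney test is then 2[1 − Φ(1.96/√(1 − r))].

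| ρ | 0 | 0.1 | 0.2 | 0.3 |
|---|---|---|---|---|
| r | 0 | 0.096 | 0.191 | 0.288 |
| Size, formula | 5.0% | 3.9% | 2.9% | 2.0% |
| Size, simulated (1:1, 10,000 datasets) | 4.8% | 3.8% | 3.1% | 2.0% |

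Conditional logistic regression stayed at 4.9 to 5.8% throughout.

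**Step 3: power, and the cost of incomplete pairs.** With loss l per arm, a 1:1 pair survives with probability (1 − l)²: 64 of 100 pairs at 20% and 49 at 30%. Simulated power at 0.3 SD, Mann-Whitney / conditional logistic, 1:1:

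| Loss per arm (pairs kept) | ρ = 0 | 0.1 | 0.2 | 0.3 |
|---|---|---|---|---|
| 0% (100) | 55.1 / 57.0 | 54.9 / 61.1 | 54.4 / 65.3 | 54.1 / 71.1 |
| 20% (64) | 45.5 / 39.6 | 45.1 / 43.2 | 44.5 / 47.2 | 44.5 / 52.4 |
| 30% (49) | 40.0 / 31.5 | 40.0 / 34.7 | 39.5 / 38.1 | 39.1 / 42.5 |

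A hand check of one cell (64 pairs, ρ = 0): Φ(0.3/√(2/64) − 1.96) = Φ(1.70 − 1.96) = 0.40, which agrees. The conditional test has less power at 20% loss with ρ of 0 to 0.1, and at 30% loss up to about 0.2.

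**Step 4: selection on SpO2.** Suppose a share q of cases lies below every control and the remaining cases do not differ from controls. The probability that a random case is below a random control is q + (1 − q)/2 = 0.5 + q/2. With 100 per arm the standard error of that estimate is √(201/(12 × 100 × 100)) = 0.0409, so rejection is about Φ(0.5q/0.0409 − 1.96).

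| q | 10% | 15% | 25% | 50% |
|---|---|---|---|---|
| Formula, 1:1 | 23% | 45% | 86% | 100% |
| Simulated, 1:1 | 23% | 45% | 87% | 100% |
| Simulated, 1:2 | 30% | 56% | 93% | 100% |

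The same reasoning applies to respiratory rate, with its own share.

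**The case against.** The strongest case against acting is that this is a secondary descriptive table. Its medians and proportions are correct whichever test is used, no decision rule rests on its p-values, and the error is in the conservative direction. At a correlation of 0 to 0.1 the true size is 5.0 to 3.9%, and with complete 1:1 pairs the power difference is 2 to 6 points. If pairs are lost, conditional regression can have less power than the planned test. All of this stands, and it is why the point is minor. It does not remove the inconsistency with the rest of the SAP or the uninformative p-values on defining signs.

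Four stronger readings are tempting, and the documents do not support them:

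- **That ignoring the matching creates false positives.** With positive correlation it does the reverse.
- **That the loss is severe because the protocol assumes a correlation of 0.7.** That value describes log antibody level and cannot be carried over to weight, temperature or symptoms.
- **That the respiratory rate and SpO2 results are fixed in advance.** A case may qualify on one sign alone, so separation on each measurement is forced only in part. The documents give no share, and at 10 to 15% rejection is 23 to 45%.
- **That the symptom rows are either decided by selection or barely touched by it.** Fever, cough and dyspnea appear in the case definition and controls may also be symptomatic, but nothing in the documents lets the effect be sized.

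The malaria present versus absent contrast is not a matched one, so the matching argument does not apply to it.

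**Conclusion.** The point holds, with minor severity. The tests named for cases versus controls do not respect the matching and have the wrong size whenever within-set correlation is positive: 3.9 to 2.0% instead of 5% at assumed correlations of 0.1 to 0.3, and no error at zero. Real differences may be missed, false positives are not inflated, and the loss may be small. P-values for respiratory rate and SpO2 partly or largely restate the eligibility rules, depending on the unknown share of cases qualifying on each sign. SAP section 8 names tests rather than p-values, and it does not single out these two variables. The claim rests on reading its tests as applying to the whole list in SAP 4.2. The primary analysis is not affected.

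**What to change.** In SAP section 8, for cases versus controls, give description only, as protocol 7.2 does. If tests are kept, replace Fisher, chi-square and Mann-Whitney for this contrast by conditional logistic regression on the matched sets, and report the number of sets kept for each row. In either case, report respiratory rate and SpO2 without p-values, and footnote that fever, cough and dyspnea are part of the case definition.

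The cost is one or two sentences and two table footnotes, to be made before the SAP is finalised. Description only needs no new code. Conditional regression is already the SAP's standard model, but a 1:1 pair is dropped when either member is missing or excluded (SAP 6.2 and 11). What it buys is correct test size and consistency with the rest of the plan. A power gain depends on correlation and loss and should not be promised. Where a sign occurs in no control, the conditional estimate is infinite and an exact or penalised version is needed.
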